8.3.3 Exploratory Endpoint(s)

8.3.3.1 Biomarkers

Biomarkers endpoints from peripheral blood may include measures such as levels of soluble factors, as well as activation and proliferation of subsets of immune cells including but not limited to subset of T cells characterized by immunophenotyping, at each scheduled time point. Biomarker endpoints from tumor biopsies may include, but will not be limited to, [REDACTED]

8.3.3.3 Other Efficacy Endpoints

PFS based on Lugano (2014) Criteria:

PFS for a subject is defined as the time from the first dosing date to the date of first progressive metabolic disease or death due to any cause (death occurring after retreatment will not be considered), whichever occurs first. Subjects who died without a reported prior progression will be considered to have progressed on the date of their death. The censoring rules applied to the PFS endpoint based on the IWG criteria will also be used for this endpoint.

Complete Metabolic Response Rate based on Lugano 2014 Criteria:

The CMR rate is defined as the number of subjects with a BOR of CMR based on the Lugano (2014) criteria divided by the number of treated subjects. The duration of CMR (DoCMR) will only be evaluated in subjects with BOR of CMR and is defined as the time from first documentation of CMR (the date of first negative FDG-PET scan) to the date of initial objectively documented PMD based on the Lugano (2014) criteria or death due to any cause, whichever occurs first. Censoring will be applied using the DOR definition. CMR rate and DoCMR will be evaluated based on investigator assessments.

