- Safety outcome measures: Safety assessments will be based on medical review of AE reports and the results of vital sign measurements, electrocardiograms (ECGs), physical examinations, pulse oximetry, and clinical laboratory tests. AEs will be assessed continuously during the study and for 135 days after the last treatment. AEs will be coded using the most current version of Medical Dictionary for Regulatory Activities (MedDRA) and reviewed for potential significance and importance. AEs and laboratory tests will be graded using the NCI CTCAE v4.0.
- Efficacy measures: Tumor responses will be determined for subjects with adequate data as defined by the following efficacy criteria.
 - NHL and HL subjects: Revised Response Criteria for Malignant Lymphoma ([Appendix 1](#))
 - NHL or HL subjects who had FDG-PET scans performed in the pre-treatment period and during this study: retrospective assessment using Lugano 2014 Response Criteria ([Appendix 7](#))
 - CLL subjects: Guidelines for the Diagnosis and Treatment of Chronic Lymphocytic Leukemia ([Appendix 2](#))
 - MM subjects: Response Criteria Modified from IMWG for Multiple Myeloma ([Appendix 6](#))
- Pharmacokinetic measures: Serial serum samples will be collected from all subjects at specified time points to evaluate concentrations of relatlimab and/or nivolumab. PK parameters such as C_{max}, C_{trough}, T_{max}, AUC(TAU), CLT, and AI will be derived from serum concentration versus time data.
- Immunogenicity measures: Serum samples will be collected from all subjects at specified time points to evaluate development of anti-drug antibodies (ADA) to relatlimab and/or nivolumab.
- Exploratory Biomarker measures: The sample collection and biomarker assessment strategy is designed to address mechanisms of action, pharmacodynamic changes associated with relatlimab administered as monotherapy or in combination with nivolumab, and potential identification of predictive safety and efficacy biomarkers associated with relatlimab, and to evaluate potential mechanisms of resistance to relatlimab. To address these key questions, peripheral blood, serum, and biopsy samples will be collected prior to and during study drug treatment in Parts A, B, C, and D, of this study.

Statistical Considerations:

Sample Size:

Dose escalation (Part A and C): The sample size at each dose depends on observed toxicity and cannot be precisely determined. Part A will have ■ to ■ subjects in each cohort.

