5.4 Efficacy Assessments

Study evaluations will take place in accordance with the Schedule of Activities in [Section 5.1](#).

Efficacy assessments will be conducted and reported by the investigator on the CRF using the appropriate efficacy assessment based on tumor type.

- Subjects with NHL or HL will be evaluated using the 2007 IWG Response Criteria for Malignant Lymphoma⁶² ([Appendix 1](#)). Disease assessments for subjects with HL and DLBCL will occur between Days [] and [] of each treatment cycle [] (cycles) and at the [].
- Since the conception of this protocol, new response criteria known as Lugano 2014 criteria ([Appendix 7](#)) have been developed to refine tumor metabolic response. A retrospective exploratory assessment of tumor metabolic response will be evaluated according to the Lugano 2014 criteria using the Deauville 5-point scale on Part D subjects with NHL or HL who had fluorodeoxyglucose (FDG)-positron emission tomography (PET) scans performed in the pre-treatment period (defined as within 60 days before the first dose, providing no other therapy was given during this time) and during this study.
 - For these PET-based assessments, a response of complete metabolic response (CMR), partial metabolic response (PMR), no metabolic response, or progressive metabolic disease (PMD) will be determined. The PET scan metabolic uptake will be graded using the Deauville 5-point scale, with a score of 1, 2, or 3 considered to represent a CMR (see [Appendix 7](#)). Assessments will be performed by PET scan with CT/MRI of diagnostic quality, with disease involvement determined by focal FDG uptake in nodal and extranodal lesions (including the spleen and liver).
- Subjects with CLL will be evaluated using the 2008 IWG Response Criteria for CLL with Modifications⁶⁴ ([Appendix 2](#)). Disease assessments for subjects with CLL will occur between Days [] and [] of each treatment cycle (up to twelve 8-week treatment cycles) and at the [].
- Subjects with MM will be evaluated using Response Criteria Modified from IMWG for Multiple Myeloma⁶³ ([Appendix 6](#)).^{65,66} Disease assessments for subjects with MM will occur on Day [] and Day [] of each cycle and at the []. According to study design, the results on [] will be used to define continuation of therapy or not in all subjects.

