8.3.2.3 Efficacy

All efficacy analyses will be based on the all treated analysis population except otherwise stated. Co-primary, secondary and exploratory efficacy endpoints for Part D subjects are as follows:

Objective Response Rate (ORR)

ORR based on investigator assessment, according to the applicable criteria based on tumor type, will be co-primary endpoint in Part D. For the NHL and HL subjects, the ORR will be based on the IWG (2007) response criteria. In addition to the primary ORR endpoint, an exploratory endpoint of ORR based on the Lugano (2014) response criteria in the NHL and HL subjects in Part D will be assessed. For the Lugano criteria, response is defined as CMR and PMR.

Duration of Objective Response (DOR)

DOR is defined as the time between the date of first documented response (CR or PR) to the date of the first objectively documented progression as per criteria relevant to each disease type in Part D (Appendices 1, 2, and 6), or death due to any cause, whichever occurs first. For subjects who neither progress nor die, DOR will be censored on the date of their last tumor assessment. Subjects who start subsequent therapy without a prior reported progression will be censored at the last tumor assessments prior to initiation of the subsequent anticancer therapy. This endpoint will only be evaluated in subjects with objective response of CR or PR. DOR will be evaluated based on investigator assessments. DOR is a co-primary endpoint in Part D. DOR based on the Lugano (2014) response criteria, response defined as CMR or PMR, will be assessed for the NHL/HL subjects in Part D as an exploratory endpoint.

Complete Response (CR) Rate and Duration

The CR rate is defined as the number of subjects with a best overall response (BOR) of CR according to the applicable criteria based on tumor type, based on IWG criteria for NHL and HL subjects, divided by the number of treated subjects. The duration of CR (DoCR) will only be evaluated in subjects with BOR of CR and is defined as the time from first documentation of CR (the date of first negative FDG-PET scan) to the date of initial objectively documented progression as determined using the applicable criteria based on tumor type or death due to any cause, whichever occurs first. Censoring will be applied as per DOR definition. CR rate and DoCR will be evaluated based on investigator assessments. CR rate is an exploratory endpoint in this study.

Progression Free Survival (PFS) Rate

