APPENDIX 7 LUGANO 2014 RESPONSE CRITERIA

For PET-based assessments, a clinical response of progressive metabolic disease (PMD), no metabolic response (NMR), partial metabolic response (PMR), or complete metabolic response (CMR) will be determined. PMD/PD includes radiological evidence of progression per Lugano Classification Revised Staging System for malignant lymphoma. The PET scan metabolic uptake will be graded using the Deauville 5-point scale, with a score of ≤ 3 considered to represent a CMR.

Deauville 5-point scale: 1- no uptake above background; 2- uptake \leq mediastinum; 3- uptake $>$ mediastinum but \leq liver; 4= uptake moderately $>$ liver; 5- uptake markedly higher than liver and/or new lesions; X- new areas of uptake unlikely to be related to lymphoma.

Table 1: CMR / CR		
Response/Site	FDG PET-CT-Based (Complete Metabolic Response)	CT-Based (CR)^a All of the following:
Lymph nodes and extralymphatic sites	Score 1, 2 or 3 with or without a residual mass on 5-Point-Scale It is recognized that in Waldeyer's ring or extranodal sites with high physiologic uptake or with activation within spleen or marrow (eg, with chemotherapy or myeloid colony-stimulating factors), uptake may be greater than normal mediastinum and/or liver. In this circumstance, complete metabolic response may be inferred if uptake at sites of initial involvement is no greater than surrounding normal tissue even if the tissue has high physiologic uptake.	Target nodes/nodal masses must regress to ≤ 1.5 cm in LDi No extralymphatic sites of disease
Non-measured lesion	Not applicable	Absent
Organ enlargement	Not applicable	Regress to normal
New lesions	None	None
Bone marrow	No evidence of FDG-avid disease in marrow	Normal by morphology; if indeterminate, IHC negative

^a CT-Based could also apply to MRI-Based

Note: Cheson BD, Fisher RI, Barrington SF, et al: Recommendations for initial evaluation, staging, and response assessment of Hodgkin and non-Hodgkin lymphoma: the Lugano classification. J Clin Oncol. 2014;32:3059-68.

Table 2: PMR / PR		
Response/Site	FDG PET-CT-Based (Partial Metabolic Response)	CT-Based (PR)^a All of the following:

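### Lugano response can be assessed only in Part D subjects with qualifying PET scans but is divided by all treated subjects, so the IWG–Lugano comparison partly reflects PET availability.

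*Combined protocol and SAP*

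**What the plan says.** **Who is assessed.** Section 5.4 applies the retrospective Lugano review to "Part D subjects with NHL or HL who had fluorodeoxyglucose (FDG)-positron emission tomography (PET) scans performed in the pre-treatment period", a period "defined as within 60 days before the first dose, providing no other therapy was given during this time", and also requires PET during the study. The synopsis (Study Assessments) repeats the restriction without the 60-day window: "NHL or HL subjects who had FDG-PET scans performed in the pre-treatment period and during this study: retrospective assessment using Lugano 2014 Response Criteria". All three Part D cohorts are HL or DLBCL, so disease type excludes nobody and PET availability is the only filter.

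**What they are divided by.** Section 8.3.3.3 and the synopsis define the CMR rate as the number with "a BOR of CMR based on the Lugano (2014) criteria divided by the number of treated subjects". For Lugano ORR, Section 8.3.2.3 counts complete and partial metabolic response (CMR and PMR) and names no denominator. The general rule at the head of that section then applies: "All efficacy analyses will be based on the all treated analysis population except otherwise stated".

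**Populations.** Section 8.2 defines All Treated by one dose, with no PET condition. It defines no PET-evaluable set, and no rule says how a treated subject without the scans is to be classified under Lugano.

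**Purpose.** The rationale for Revised Protocol 09 gives a clinical interest in comparing response under IWG 2007 and Lugano 2014 as the reason for adding the Lugano analyses.

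**The concern.** The numerator can come only from subjects with the required scans, while the denominator is everyone dosed. A subject without a qualifying baseline PET is a Lugano failure by construction, whatever happened to the disease.

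The IWG side does not carry the same penalty. Appendix 1 provides for patients with no pre-treatment PET. In typically FDG-avid lymphoma a CR is allowed if the residual mass is PET negative after treatment, and a PR can also be assigned. Where avidity is variable or unknown, CT criteria apply. The same person can therefore be an IWG responder and be barred from being a Lugano responder.

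What is at stake is the reading of the comparison. A lower Lugano rate could mean that the metabolic criteria are stricter, or only that some subjects had no usable scan. The tables as planned cannot separate the two.

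**Working it through.** The plan states no Lugano rate and no share with PET, and the Part D cohort sizes are redacted, so there is no figure to reproduce. The check is a denominator identity with assumed inputs.

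**1. Identity.** Let N be the treated subjects, n those with the qualifying PET pair, x the Lugano responders, p = x/n and f = 1 − n/N. Then

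all-treated rate = x/N = p × (1 − f), and shortfall against p = p × f.

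**2. Gap between criteria.** Suppose IWG and Lugano agree perfectly in the n assessable subjects, and let r be the IWG response rate among the others. The all-treated IWG rate is p(1 − f) + r × f, so the apparent IWG–Lugano gap is r × f. It equals p × f if r = p. It is smaller if those without the scan pair are mostly early failures, and zero if r = 0.

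**3. Numbers.** f is assumed at 5% to 40%. For p I take an assumed 50%, plus the CR rate (4/23 = 17.4%) and response rate (20/23 = 87.0%) of the completed Phase 1 nivolumab HL study in Section 1.7.3.2. Those two only set a scale; they are not forecasts of Lugano rates here.

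| p | f = 5% | 10% | 20% | 30% | 40% |
|---|---|---|---|---|---|
| 17.4% | 16.5% | 15.7% | 13.9% | 12.2% | 10.4% |
| 50.0% | 47.5% | 45.0% | 40.0% | 35.0% | 30.0% |
| 87.0% | 82.6% | 78.3% | 69.6% | 60.9% | 52.2% |

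The shortfall runs from about 1 to 7 points at 17.4%, 2.5 to 20 points at 50%, and 4 to 35 points at 87%.

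**4. Effect of the denominator.** Take an assumed N = 40: 36 with a qualifying baseline PET, 32 of them also with an on-study PET, and 16 CMR. Intervals are Clopper-Pearson 95%, as in Section 8.4.2.

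- All treated: 16/40 = 40.0% (24.9 to 56.7).
- Qualifying baseline PET, missing on-study PET counted as non-response: 16/36 = 44.4% (27.9 to 61.9).
- PET pair only: 16/32 = 50.0% (31.9 to 68.1).

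The second line removes the part that is structural, since no baseline scan means no possible Lugano response. It keeps early failures in the denominator, which the third line does not. The interval widens from 31.8 to 34.0 points.

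**5. Could the CT-based columns of Appendix 7 help?** No. Section 5.4 describes a PET-based assessment and Section 8.3.2.3 counts only CMR and PMR, so subjects without PET stay unassessable.

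**The case against.** **The convention is normal.** Counting unassessed treated subjects as non-responders is a common conservative choice. It matches the IWG CR rate and the primary population, and avoids selecting subjects by scan availability. This stands as a reason to keep the all-treated rate. It does not make the comparison clean, because the penalty falls unequally on the two criteria.

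**Lugano ORR may already be excepted.** The default yields where something else is stated, and the Section 5.4 restriction could be read as such a statement. For ORR this is arguable, which is itself a reason to name the denominator. For CMR the text is explicit.

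**PET may be nearly complete.** The screening table (Table 5.1-1) lists a PET or PET/CT row for lymphoma. Its timing and notes are not visible, so f could be close to zero. The retrospective wording, limited to those who had scans, allows for a subset but does not prove a large one.

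**CR against CMR may differ less than ORR.** Section 8.3.2.3 dates CR from the first negative FDG-PET, so many IWG complete responders will have an on-study PET. They may still lack the baseline scan.

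**Little depends on it.** The Lugano endpoints are exploratory, no formal comparison is planned, and co-primary ORR and DOR use IWG. All of this stands and limits the weight of the point.

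**A stronger reading: Lugano PFS is biased upwards.** A reader might infer this because Section 8.3.3.3 counts progressive metabolic disease and adds that "death occurring after retreatment will not be considered", a clause absent from the IWG definition. CT progression followed by re-challenge and death would then seem to be no event. The documents do not support that. Appendix 7 says "PMD/PD includes radiological evidence of progression"; re-challenge under Section 3.1.5 requires confirmed progression, so the event would normally come first; and Lugano PFS adopts the IWG censoring rules. Only unclear wording remains.

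**Conclusion.** The mismatch is in the current text, in both body and synopsis. The set that can supply Lugano responders is narrower than the denominator, and IWG response is not restricted in the same way, so the IWG–Lugano comparison partly measures PET availability.

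The size cannot be found from the documents. The shortfall in the all-treated Lugano rate is p × f. Reading that as the gap against IWG also assumes that subjects without the scans would respond under IWG at the same rate. With everyone scanned, the shortfall is zero.

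The harm is to the descriptive reading of exploratory endpoints. Nothing here touches the co-primary analyses, and no bias in Lugano PFS is claimed. The change is worth making because it is cheap and makes the comparison interpretable.

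**What to change.** 1. In Section 8.2, define a Lugano-evaluable set: treated Part D NHL/HL subjects with a baseline PET that meets Section 5.4. Count every subject in it without an on-study PET as a non-responder, whether the reason is early progression, death or anything else.
2. Report CMR, PMR and Lugano ORR in that set, with the number excluded for lack of a qualifying baseline PET. Also give the number counted as non-responders for lack of an on-study PET, so that any remaining effect of scan availability is visible.
3. Cross-tabulate IWG against Lugano response in the same set.
4. Keep the all-treated rate, labelled as the conservative version, and state the denominator of Lugano ORR.
5. In the Lugano PFS definition, cross-refer to Appendix 7 so that radiological progression counts as an event, and reconcile the wording on deaths after retreatment with the IWG PFS rule.

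The cost is protocol or SAP wording and one or two tables, with no new scans or readers. The drawback is a smaller n and wider intervals, as in step 4 of the working.

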8.4 Analyses

Unless otherwise specified, safety data from Parts A-D will be summarized both (1) overall by dose level and across all dose levels and (2) by dose level and across all dose levels within each tumor type. Efficacy data will be summarized by dose level within each tumor type and patient population.

8.4.1 Demographics and Baseline Characteristics

Frequency distributions of gender and race will be tabulated. Summary statistics for age, body weight, height, and body mass index (BMI), and baseline laboratory results will be tabulated. Baseline disease characteristics will be summarized for expansion cohorts for different disease cohorts separately, as appropriate.

8.4.2 Efficacy Analysis

Individual ORR, CR rate, DOR, CMR, PMR, and PFS (based on IWG and Lugano criteria) will be determined. BOR outcomes will be summarized using frequency tables together with 2-sided 95% confidence intervals. Time to event distribution (eg, PFS, DOR, and DoCMR) will be estimated using Kaplan-Meier (K-M) method. When appropriate, the median along with 95% CI will be provided using Brookmeyer and Crowley methodology (using log-log transformation for constructing the confidence intervals). Rates at fixed time points (eg, PFSR 24 weeks) will be derived from the K-M estimate and corresponding confidence interval will be derived based on Greenwood formula. Confidence intervals for binomial proportions will be derived using the Clopper-Pearson method. OS data will be analyzed similarly to PFS data analysis.

8.4.3 Safety Analyses

All subjects who receive study drug therapy will be evaluated for safety endpoints. All recorded AEs will be coded according to the most current version of MedDRA and be graded using the NCI CTCAE version 4.0. AEs will be listed and subjects with AEs will be summarized based on the event with worst CTC grade by system organ class (SOC) and preferred term (PT), counting once at the PT term level and once at the SOC level, for each dose, dosing regimen, and overall. Vital signs and clinical laboratory test results will be listed and summarized by treatment. In addition, the worst grade of a laboratory measure observed on-study by the baseline grade (per CTCAE v 4) will also be generated for selected laboratory tests. Any significant physical examination findings and results of clinical laboratory tests will be listed. ECG results will be evaluated by the investigator and abnormalities, if present, will be listed.

8.4.4 Pharmacokinetic Analyses

PK parameters for relatlimab as monotherapy and in combination with nivolumab will be calculated using noncompartmental analyses. Summary statistics will be tabulated for the PK parameters of relatlimab by treatment and study day/week. To describe the dependency on dose of relatlimab, scatter plots of C_{max} and AUC (TAU) versus dose may be provided for each day measured. Dose proportionality of relatlimab will also be assessed based on a power model.

Summary statistics of nivolumab exposure at trough and end of infusion will be tabulated separately.

8.4.5 Exploratory Biomarker Analyses

The pharmacodynamic effect on [REDACTED] in subjects who undergo biopsy will be summarized using summary statistics and plots. In addition, the correlation of [REDACTED] changes and tumor marker expression with measures of peripheral blood markers may be explored graphically, and using appropriate modeling approaches based on data availability. Associations of biomarker measures from peripheral blood or tumor biopsy with clinical outcomes may also be explored graphically and further assessed as needed by methods such as, but not limited to, logistic regression and characterized by appropriate statistics.

8.4.6 Outcomes Research Analyses

Not applicable.

8.4.7 Other Analyses

8.4.7.1 Immunogenicity Analyses

A listing will be provided for all available immunogenicity data. The number and percent of subjects who meet specified endpoint definitions in the statistical analysis plan (SAP) will be summarized for each drug. To examine the potential relationship between immunogenicity and safety, a table summarizing the frequency and type of AEs of special interest may be explored by immunogenicity status. In addition, potential relationships between immunogenicity and efficacy, pharmacodynamic markers, and/or PK may also be explored.

